## 2.2. Secondary Objectives

- To evaluate time-to-progression (TTP)
- To evaluate progression-free-survival (PFS)
- To evaluate overall-survival (OS)
- To evaluate safety

## 3. PATIENT ELIGIBILITY AND WITHDRAWAL CRITERIA

### 3.1. Inclusion Criteria

1. Eligible participants must have multiple myeloma using standard criteria (Appendix B).
2. Patients must have measurable disease requiring systemic therapy defined as at least one of the following:
  - Serum M-protein  $\geq 0.5$  g/dl ( $\geq 5$  g/l)
  - Urine M-protein  $\geq 200$  mg/24 hrs
  - Serum free light chain assay: involved free light chain level  $\geq 10$  mg/dl ( $\geq 100$  mg/l) provided the serum free light chain ratio is abnormal
3. Must have progressed during or after at least one previous bortezomib-containing treatment regimen. Patients who have received previous high-dose therapy/autologous stem cell transplantation are eligible.
4. Eastern Cooperative Oncology Group (ECOG) performance status of 0-2. (see Appendix A).
5. Must meet the following laboratory criteria:
  - Absolute neutrophil count (ANC)  $\geq 1000/\mu\text{L}$ ;
  - Platelets  $\geq 70,000/\mu\text{L}$ ;
  - AST or ALT and alkaline phosphatase (ALP) must be  $\leq 2.5$  x ULN, or  $\leq 5$  x ULN in patients with plasmacytomas of the liver;
  - Total bilirubin  $\leq 1.5$  x the institutional ULN;
  - Serum creatinine  $\leq 1.5$  x ULN or calculated creatinine clearance  $\geq 50$  ml/min;
  - Serum potassium, calcium, magnesium WNL (These may be corrected prior to starting therapy, to make the patient eligible.)
6. Ability to swallow oral medications.
7. Baseline MUGA or ECHO must demonstrate left ventricular ejection fraction (LVEF)  $\geq$  the lower limit of the institutional limits of normal.

8. Male or females  $\geq 18$  years of age.
9. Female patients must not be of childbearing potential or must agree to use adequate contraceptive measures.
10. Male patients willing to use adequate contraceptive measures.
11. Willingness and ability to comply with the trial and follow-up procedures.
12. Ability to understand the nature of this trial and give written informed consent.

### **3.2. Exclusion Criteria**

1. Currently receiving or have received systemic cancer therapy (chemotherapy, biologic therapy)  $\leq 21$  days of initiating study therapy. For patients receiving small molecule targeted therapy, study treatment may begin  $>21$  days after last dose or  $>5$  half lives of previous treatment, whichever is shorter. Patients must have completed radiation therapy  $\geq 7$  days prior to starting study treatment. Patients must have recovered from or come to a new chronic stable baseline from all treatment-related toxicities. Dexamethasone or other high-dose steroid therapy must be stopped  $\geq 7$  days prior to starting study treatment.
2. Previous treatment with HDAC, DAC, HSP90 or valproic acid for treatment of cancer.
3. Requires valproic acid for any medical condition during the study  $\leq 5$  days prior to first panobinostat treatment.
4. Patient has not recovered from all therapy-related toxicities associated with prior treatments to  $<$  Grade 2 CTCAE.
5. Known history of allergy to Captisol® (a cyclodextrin derivative used to solubilize carfilzomib).
6. Patients with pleural effusions requiring thoracentesis or ascites requiring paracentesis  $\leq 14$  days prior to study entry.
7. Patients using medications that have a risk of prolonging the QT interval or inducing Torsade de Pointes if treatment cannot be discontinued or switched to a different medication prior to receiving study drug (see Appendix F).
8. Patients with  $>$  grade 2 diarrhea.
9. Patients with impaired cardiac function, including any of the following conditions:
  - History or presence of sustained ventricular tachyarrhythmia.
  - Any history of ventricular fibrillation or Torsade de pointes.
  - Bradycardia defined as HR  $< 50$  bpm. Patients with pacemakers are eligible if HR  $\geq 50$  bpm.
  - Screening ECG with a QTc  $> 450$  msec.
  - Right bundle branch block + left anterior hemiblock (bifascicular block).
  - Patients with myocardial infarction or unstable angina  $\leq 6$  months prior to starting study drug.

- Other clinically significant heart disease (e.g. CHF NY Heart Association class III or IV (Appendix D), uncontrolled hypertension, history of labile hypertension, or history of poor compliance with an antihypertensive regimen).
10. Infection requiring IV antibiotics.
  11. Patients with > grade 2 peripheral neuropathy or with uncontrolled pain.
  12. Women who are pregnant or lactating.
  13. Any concurrent medical illness that may impair the ability of the patient to tolerate study treatment and comply with the requirements of the study.
  14. Mental condition that would prevent patient comprehension of the nature of, and risk associated with, the study.
  15. Use of any non-approved or investigational agent  $\leq 30$  days prior to administration of the first dose of study drug. Patients may not receive any other investigational or anti-cancer treatments while participating in this study.
  16. Presence of other active cancers, or history of treatment for invasive cancer  $\leq 5$  years. Patients with stage I cancer who have received definitive local treatment at least 3 years previously, and are considered unlikely to recur are eligible. All patients with previously treated in situ carcinoma (i.e. non-invasive) are eligible, as are patients with history of non-melanoma skin cancer.

### **3.3. Withdrawal Criteria**

Patients will be discontinued from study treatment for any of the following reasons:

- Disease progression
- Irreversible or intolerable toxicity or abnormal laboratory values thought to be related to drug toxicity
- Patient requests to withdraw from the trial and discontinue treatment
- Patient requests to discontinue treatment
- Pregnancy (see Section 3.3.1)
- Inability of the patient to comply with trial requirements
- Conditions requiring therapeutic intervention not permitted by the protocol
- Intercurrent illness (this will be at the investigator's discretion)
- Non-compliance/lost to follow-up

Patients who have been discontinued from trial treatment will not be replaced. After withdrawal from protocol treatment, patients must be followed for AEs for 30 calendar days after their last dose of trial drug. All new AEs occurring during this period must be reported and followed until resolution, or after 30 days (whichever comes first), unless, in the opinion of the investigator, these values are not likely to improve because of the underlying disease. In this case, the investigators must record his or her reasoning for

this decision in the patients' medical records and as a comment on the Case Report Form (CRF).

All patients who have CTCAE grade 3 or 4 laboratory abnormalities at the time of withdrawal must be followed until the laboratory values have returned to grade 1 or 2, or 30 days after the date of withdrawal (whichever comes first), unless it is, in the opinion of the investigator, not likely that these values are to improve because of the underlying disease. In this case, the investigator must record his or her reasoning for making this decision in the patients' medical records and as a comment on the CRF.

### **3.3.1. Pregnancy**

During the course of the trial, all female patients of childbearing potential must contact the treating investigator immediately if they suspect that they may be pregnant (a missed or late menstrual period should be reported to the treating investigator).

If an investigator suspects that a patient may be pregnant prior to administration of trial drug(s), the trial drug(s) must be withheld until the result of the pregnancy test is confirmed. If a pregnancy is confirmed, the patient must not receive any trial drug(s), and must be discontinued from the trial.

If an investigator suspects that a patient may be pregnant after the patient has been receiving trial drug(s), the trial drug(s) must immediately be withheld until the result of the pregnancy test is confirmed. If a pregnancy is confirmed, the trial drug(s) must be immediately and permanently stopped, the patient must be discontinued from the trial, and the investigator must notify the SCRI Innovations study chair as soon as possible. If a patient becomes pregnant while enrolled in the trial, a Pregnancy Form (a paper report form, not available within EDC system) should be completed and faxed to the sponsor or designee. For more details regarding handling and reporting of pregnancies that occur during treatment, see Section 11.5.

## **4. STUDY REGISTRATION**

The patient must willingly consent after being informed of the procedures to be followed, the experimental nature of the treatment, potential benefits, alternatives, side-effects, risks and discomforts. Human protection committee approvals of this protocol and consent form are required prior to patient enrollment. Registration must occur prior to the initiation of protocol therapy.

Eligible patients will be enrolled through SCRI Innovations. Participating sites may call [name] for assistance, or fax a completed and signed Enrollment Form to the SCRI Innovations Enrollment Desk. The SCRI Innovations fax registration number is [contact] and is available, Monday through Friday, 8:30 a.m. to 4:30 p.m., Central Standard Time. Patient registration will be confirmed via fax within 24 hours, or by the next business day.

## 5. STUDY DESIGN

This is an open-label, non-randomized Phase I/II study of patients with relapsed or refractory multiple myeloma.

The Phase I study will determine the MTD of the combination of carfilzomib and panobinostat. The Phase I portion will follow a standard dose escalation design, beginning with dose level 1 (see Table 2). Patients will be assessed for dose-limiting toxicity (DLT) at each visit during Cycle 1 prior to receiving treatment. Dose modifications will not be permitted during Cycle 1 unless a patient experiences a DLT (see Section 5.2.2.). Treatment cycles will be administered at 28-day intervals. Panobinostat will be administered orally three times weekly during weeks 1 and 3 of each cycle (Days 1, 3, 5, 15, 17, 19). Carfilzomib will be administered intravenously on Days 1, 2, 8, 9, 15, and 16 of each cycle. During Cycle 1, the carfilzomib dose will be escalated after the Day 2 dose, if well tolerated.

A maximum of four dose levels were evaluated. No DLTs were seen during the Phase I portion.

In the Phase II portion of this study, patients with relapsed/refractory multiple myeloma will receive treatment with the dose level 4 panobinostat and carfilzomib combination. Patients will be reevaluated for response to treatment after each cycle (4 weeks). Patients with objective response or stable disease will continue treatment, with subsequent reevaluations every 4 weeks, until disease progression or unacceptable toxicity occurs.

[figure not shown]
A parallel Phase I study will occur to evaluate a minimum of 3 patients and a maximum of 6 patients following a standard dose escalation design at additional dose levels of the combination of carfilzomib and panobinostat (see Table 3).

If additional dose levels are found to be tolerable, then additional patients will be recruited into an expansion cohort which will be open at all sites - a maximum total of 36 patients (including the ones recruited into the parallel Phase I study) will be treated at this dose level. Sites will be notified about the expansion cohort and patients will enter in the dose level confirmed in their enrollment confirmation from SCRI Innovations.

Up to 80 eligible patients will be treated in the Phase I/II study. The treatment schema for the study is shown in Figure 2.

Figure 2

Treatment Schema

## **5.1. Treatment Plan**

Panobinostat and carfilzomib will be administered in the Phase I and Phase II portions of this trial as follows:

### **5.1.1. Panobinostat**

#### **PO TIW during weeks 1 and 3 of each 28-day cycle (i.e. D1, 3, 5, 15, 17, 19)**

Dose levels are defined in Table 2.

Panobinostat will be self-administered (by the patient). Patients should be instructed to take their once-a-day oral dose of panobinostat at the same time of each scheduled treatment day. Panobinostat should be taken with a glass of water; the entire dose should be taken over as short a time as possible. Patients should swallow the capsules as a whole and should not chew them. Patients must avoid grapefruit or grapefruit juice and Seville (sour) oranges during the entire study.

If the patient forgets to take his/her dose, the patient may be instructed to take the dose up to 12 hours after the usual time. If more than 12 hours have passed, then the dose should be withheld that day. The patient should be instructed to wait until the next scheduled dose. If vomiting occurs, no attempt should be made to replace the vomited dose. No missed doses should be made-up.

#### **5.1.1.1. Panobinostat Administration – Electrolyte Monitoring and Cardiac Precautions**

##### **Electrolyte Monitoring**

All patients must have an assessment of serum potassium, magnesium, and calcium (total corrected for albumin, or ionized calcium)  $\leq 72$  hours prior to the administration of oral panobinostat on Day 1 of Cycle 1 and the results must all be  $\geq$ LLN before the first dose of panobinostat is administered. Throughout the study serum biochemistry values including serum potassium, calcium, phosphorus and magnesium will be monitored closely. Whenever serum potassium, calcium, phosphorus and magnesium are assessed, if the value is  $<$ LLN, then the patient's potassium, calcium, phosphorus or magnesium should be immediately supplemented following the availability of that laboratory result, in order to minimize the time patients have low values. Patients must then undergo a repeat biochemistry test to demonstrate values  $\geq$ LLN. These values must be  $\geq$  LLN before the patient is re-dosed with oral panobinostat.

Patients must be instructed to not take panobinostat if their most recent biochemistry values demonstrate potassium, calcium, phosphorus or magnesium  $<$ LLN. At a minimum, potassium, magnesium, phosphorus and calcium will be checked according to the protocol. More frequent testing should be done if clinically indicated (e.g. patient

has had prior low values; patient is taking medications that can result in lowering of their potassium, magnesium, phosphorus or calcium levels.

### ECG QTcF Monitoring

Because of the observed QTc prolongation in several patients receiving panobinostat, to be eligible for this trial, the patient must have a mean QTc interval  $\leq 450$  at baseline. During Cycle 1 of panobinostat, ECG's will be monitored intensively (see Table 1). Prior to C1D1 and C1D5 dosing of panobinostat, all patients will have 3 12-lead ECGs, separated by 5-10 minutes. Triplicate ECGs, separated by 5-10 minutes, will be repeated approximately 3 hours after panobinostat dosing on C1D1 and C1C5. See Section 6.2.1. for additional ECG monitoring guidelines. Refer to Table 6 for management of prolonged QTc interval.

Beginning Cycle 2, patients will have a single ECG prior to the Day 1 panobinostat dose (assuming no QTc prolongation occurred during Cycle 1).

**Table 1. ECG QTcF Monitoring**

CYCLE	DAY	ECG(s) Time Point
Baseline	Pre-Treatment	Single ECG to Assess Eligibility
Cycle 1	Day 1 (day of first study drug administration)	Pre-Dose : 3 ECGs (Sequential ECGs, separated by 5-10 minutes)  Post-Dose : 3 ECGs 3 hours ( $\pm$ ½ hour) after dosing (Sequential ECGs, separated by 5-10 minutes)
	Day 5	Pre-Dose : 3 ECGs (Sequential ECGs, separated by 5-10 minutes)  Post-Dose : 3 ECGs 3 hours ( $\pm$ ½ hour) after dosing (Sequential ECGs, separated by 5-10 minutes)
Cycle 2 and beyond	Day 1	Pre-Dose : Single ECG

If the patient experiences QTcF >480 msec in cycle 1 or in any subsequent cycle, then repeat the monitoring schedule until they have a cycle with no QTc prolongation.

If no significant QTcF prolongation is noted during the first 8 cycles, the QTc monitoring is no longer required and may be performed at the Investigator's discretion.

### 5.1.2. Carfilzomib

Cycle 1: TBD mg/m^2 IV Day 1, 2 then TBD mg/m^2 IV Day 8, 9, 15, 16

Cycle 2 and Beyond: TBD mg/m^2 IV Day 1, 2, 8, 9, 15, and 16

Carfilzomib will be administered over 30 minutes (see Section 6.4). Dose levels to be tested are defined in Table 2.

Treatment cycles will be repeated every 28 days. Patients will be evaluated for response to treatment every 4 weeks (i.e. after every cycle). Patients with stable disease or better may continue on study treatment until evidence of disease progression.

#### Hydration and Fluid Monitoring

**Oral hydration** - All patients must be well hydrated (i.e., volume replete). Begin oral hydration equal to approximately 30 mL/kg/day (~6–8 cups of liquid per day), starting 48 hours prior to the planned first dose of carfilzomib. Compliance must be reviewed with the patient and documented by the site personnel prior to initiating treatment with carfilzomib; treatment is to be delayed or withheld if oral hydration is not deemed to be satisfactory.

**Intravenous Fluids** - 250–500 mL of IV normal saline (or other appropriate IV fluid formulation) must be given before *and* after each carfilzomib dose during Cycle 1. If lactate dehydrogenase (LDH) or uric acid is elevated at Cycle 2, Day 1, then the recommended IV hydration should be repeated for Cycle 2 and all subsequent cycles until progression disease at the study doctor's discretion to monitor TLS. The goal of the hydration program is to maintain robust urine output, (e.g., ≥ 2 L/day). Patients should be monitored periodically during this period for evidence of fluid overload.

In patients considered to remain at risk for tumor lysis syndrome at completion of Cycle 1, hydration should be continued into Cycle 2. Patients in whom this program of oral and IV fluid hydration is contraindicated, e.g., due to pre-existing pulmonary, cardiac, or renal impairment, will not be eligible to participate in the clinical trial.

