## **6.4. Management of Carfilzomib-Related Events**

### **6.4.1. Cardiopulmonary Disorders**

New or worsening cardiac failure (e.g., congestive cardiac heart failure, pulmonary edema, and decreased ejection fraction), myocardial ischemia, and myocardial infarction have occurred following administration of carfilzomib. Death due to cardiac arrest has occurred within a day of carfilzomib administration, and fatal outcomes have been reported with cardiac failure and myocardial infarction.

While adequate hydration is required prior to dosing in Cycle 1, all subjects should be monitored for evidence of volume overload, especially subjects at risk for cardiac failure. The total volume of fluids may be adjusted as clinically indicated in subjects with baseline cardiac failure or who are at high risk for cardiac failure.

Withhold carfilzomib for Grade 3 or 4 cardiac events until recovery and consider whether to restart carfilzomib at 1 dose level reduction based on a benefit/risk assessment.

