#### **7.3.5. Cycle 2 and Beyond - Day 1, 8 and 15**

- Medical history (Day 1 only)
- Physical examination (Day 1 only)
- Measurement of vital signs (blood pressure, pulse, and respiratory rate and weight)
- ECOG PS (Day 1 only) (Appendix A)
- CBC, 3-part differential and platelets (-3 to Day 1 window allowed)
- CMP (see Section 7.1.) plus magnesium and phosphorus (Day 1 only) (-3 to Day 1 window allowed)
- Uric acid (if clinically indicated) (-3 to Day 1 window allowed)
- LDH (if clinically indicated)
- PT/PTT/INR (Day 1 only; if medically indicated or if patient is receiving warfarin or other anti-coagulant)
- 12-lead ECG (Day 1 only if no previous problems with QTc prolongation)
- Adverse event evaluation
- Record concomitant medications

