### 8.2.4. Administration

Carfilzomib for Injection is supplied as a lyophilized parenteral product in single-use vials. The lyophilized product is reconstituted with water for injection to a final carfilzomib concentration of 2.0 mg/mL prior to administration. The dose will be calculated using the subject's actual BSA at baseline. Subjects with a BSA > 2.2 m^2 will receive a dose based upon a 2.2 m^2 BSA.

At least 48 hours before Cycle 1 Day 1, **oral hydration** should be given as follows: 30 mL/kg/day (approximately 6 to 8 cups of liquid per day) continuing up to the time of treatment. Subject compliance must be assessed before initiating treatment, which is to be delayed if oral hydration is not adequate. In subjects considered at risk for TLS, oral hydration should be continued in Cycle 2 and beyond as required by the subject's medical condition and at the Investigator's discretion.

**IV hydration** will be given immediately prior to carfilzomib during Cycle 1. This will consist of 250 to 500 mL normal saline or other appropriate IV fluid. If lactate dehydrogenase (LDH) or uric acid is elevated (and/or in subjects considered still at risk for TLS) at Cycle 2 Day 1, then the recommended IV hydration should be given additionally before each dose in Cycle 2. The goal of the hydration program is to maintain robust urine output (e.g., ≥ 2 L/day). Subjects should be monitored periodically during this period for evidence of fluid overload.

If the subject has a dedicated line for carfilzomib administration, the line must be flushed with a minimum of 20 mL of normal saline prior to and after drug administration.

Carfilzomib will be given as an IV infusion over approximately 10 minutes. For doses > 27 mg/m^2, carfilzomib should be infused over 30 minutes. The dose will be administered at a facility capable of managing hypersensitivity reactions. Subjects will remain at the clinic under observation for at least 1 hour following each dose of carfilzomib in Cycle 1 and following the dose on Cycle 2 Day 1. During these observation times, **post dose IV hydration** (between 250 mL and 500 mL normal saline or other appropriate IV fluid formulation) will be given. Subjects should be monitored periodically during this period for evidence of fluid overload.

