## Appendix E: Schedule of Assessments for MM 27 Phase I Portion (continued)

---

- A The physical examination, ECOG PS, CBC, CMP, PT/INR, urinalysis, and pregnancy test should be done <7 days prior to initiation of treatment. However, if these initial examinations are obtained ≤72 hours of Cycle Day1 they do not have to be repeated.
  - B Vital signs are defined as height, blood pressure, pulse, respirations, weight. Only at the baseline visit, height will be recorded.
  - C CMP includes the following laboratory tests: glucose, BUN, creatinine, sodium, potassium, chloride, calcium, CO2, alkaline phosphatase, AST, ALT, total bilirubin, total protein, and albumin plus magnesium and phosphorus. Uric acid and LDH will also be collected during Cycle 1. Cycle 2 and beyond (and end of study) Uric acid and LDH will be obtained if clinically indicated. Labs may be obtained ≤72 hours of any or all assessments.
  - D Update of the medical history and physical examination should be obtained on D1 (+/- 72 hrs) of each cycle after Cycle 1 until progression.
  - E A serum pregnancy test will be performed **only** for women of childbearing potential (see Section 3.3.1).
  - F Evaluation should be performed at screening visit and repeated at investigator's discretion, if medically indicated. If patient is receiving warfarin or other anti-coagulant therapy, coagulation parameters should be monitored as indicated.
  - G On Cycle 1 Day 1, and Cycle 1 Day 5, three ECGs will be obtained 5-10 minutes apart before the patient takes panobinostat, and will be repeated (x 3, 5-10 minutes apart) approximately 3 hours after the panobinostat dose is taken orally.
  - H If no problems with QTc prolongation occur during Cycle 1, a single pre-dose ECG on Day 1 of each subsequent cycle is required.
  - I Oral hydration – (6-8 cups of liquid per day) starting 48 hours prior to the 1st dose of carfilzomib ( i.e. Day -2 and Day -1, Cycle 1), and prior to all carfilzomib doses during Cycle 1. In patients considered at risk for TLS, oral hydration should be continued in Cycle 2 and beyond as required by the patient's medical condition and at the study doctor's discretion.
  - J IV hydration – 250-500 mL of NS (or other IV formulation) before and after each carfilzomib dose during Cycle 1 (Days 1, 2, 8, 9, 15 and 16). If LDH or uric acid is elevated at Cycle 2, Day 1, the recommended hydration should be repeated for Cycle 2.

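### From Cycle 2 the IV hydration rules differ between Section 5.1.2, Section 8.2.4 and Appendix E footnote J, and the laboratory result that triggers them need not be measured

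*Combined protocol and SAP*

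**What the plan says.** **Cycle 1.** Section 5.1.2 (Hydration and Fluid Monitoring) states that 250 to 500 mL of IV fluid "must be given before *and* after each carfilzomib dose during Cycle 1". Section 8.2.4 and Appendix E footnote J also give fluid before and after each Cycle 1 dose.

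**Cycle 2 onward, after a raised LDH or uric acid at Cycle 2 Day 1.**
- Section 5.1.2: "then the recommended IV hydration should be repeated for Cycle 2 and all subsequent cycles until progression disease", at the study doctor's discretion.
- Section 8.2.4: "then the recommended IV hydration should be given additionally before each dose in Cycle 2". It also gives post-dose fluid during the observation hour on Cycle 2 Day 1, with no laboratory condition.
- Appendix E footnote J: "the recommended hydration should be repeated for Cycle 2".

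**Judged tumor lysis risk.** Section 5.1.2 continues hydration into Cycle 2 for patients still considered at risk when Cycle 1 ends. Section 8.2.4 adds such patients to its trigger. Footnote J does not mention them for IV fluid; footnote I does so for oral fluid only.

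**The tests.** Section 7.3.5 lists "LDH (if clinically indicated") for Cycle 2 and beyond, and uric acid on the same terms. Footnote C agrees. Footnote S leaves the repeat to the study doctor's discretion if Cycle 1 values were normal.

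**Eligibility.** Section 5.1.2 says of "Patients in whom this program of oral and IV fluid hydration is contraindicated", for example because of existing pulmonary, cardiac or renal impairment, that they may not take part. Section 3.2 and the synopsis do not list this rule.

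**The concern.** Three passages act on the same laboratory finding and prescribe different fluid programmes, so two sites that both follow the protocol could treat the same patient differently. The testing rules add a second gap: the programme depends on a result that the assessment schedule does not require.

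The protocol itself treats hydration as consequential. Section 1.3.1 reports four suspected or documented tumor lysis cases before the prophylaxis guidelines and none afterwards, and attributes a fall in severe renal impairment mainly to hydration and low-dose dexamethasone. In the other direction, Section 6.4.1 describes cardiac failure, including fatal cases, and asks for monitoring for volume overload. Tolerability of the combination is the primary safety endpoint (Section 10.5), so a multicentre study should deliver this supportive measure under one rule.

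**Working it through.** The plan states no total volume to reproduce. The check sets the passages side by side and multiplies the protocol's own volumes.

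**Inputs**
- Volume per administration: 250 to 500 mL (Sections 5.1.2 and 8.2.4, footnote J).
- Carfilzomib doses per cycle: six, on Days 1, 2, 8, 9, 15 and 16 (Section 5).
- Assumptions: all six doses are given, and repeating the recommended hydration in Section 5.1.2 and footnote J means repeating the Cycle 1 before-and-after programme.

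**Formula:** volume = number of administrations × 250 to 500 mL.

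| IV fluid | Section 5.1.2 | Footnote J | Section 8.2.4 |
|---|---|---|---|
| Triggered patient, Cycle 2 | 6 × 2 = 12; 3,000–6,000 mL | 6 × 2 = 12; 3,000–6,000 mL | 6 + 1 = 7; 1,750–3,500 mL |
| Triggered patient, each cycle from Cycle 3 | up to 12; up to 3,000–6,000 mL, at discretion | none specified | none specified |
| Patient with no trigger and not judged at risk, Cycle 2 | 0 | 0 | 1; 250–500 mL, after the Day 1 dose |

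In Cycle 2 the gap for a triggered patient is 12 − 7 = 5 administrations, or 5 × 250 to 500 mL = 1,250 to 2,500 mL.

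**Trigger against schedule.** All three texts name a Cycle 2 Day 1 result.
1. Section 7.3.5 and footnote C: both tests from Cycle 2 only when clinically indicated, whatever the Cycle 1 values.
2. Footnote S, attached to the Cycle 2 entry in the schedule grid: discretionary if Cycle 1 values were normal, which implies a repeat if they were not.
3. No passage expressly requires the tests at Cycle 2 Day 1.

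A site can therefore comply with the schedule and never learn whether the laboratory trigger was met. The testing rules also differ among themselves for a patient whose Cycle 1 values were abnormal.

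**Entry routes.** Sections 5.1.2 and 8.2.4 allow two routes to Cycle 2 IV fluid, the laboratory result or judged risk. Footnote J gives one. A patient judged at risk with normal or unmeasured values gets Cycle 2 IV fluid under Section 8.2.4, and hydration under Section 5.1.2, but no IV fluid under footnote J.

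**The case against.** Several limits on the point are fair, and they rule out stronger readings.

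- **Later cycles are discretionary.** A reader might infer that Section 5.1.2 mandates fluid indefinitely. It does not: the sentence ends with the study doctor's discretion. A Cycle 2 to 6 comparison of 15 to 30 L (5 × 3 to 6 L) with 1.75 to 3.5 L would contrast a ceiling with a floor. It assumes that discretion is always exercised and no dose is missed, and it sets aside Section 6.4.4, which asks for adequate hydration after Cycle 1 as needed. Discretion softens the conflict over duration but does not remove it, because the other two texts do not extend IV fluid past Cycle 2.
- **Cycle 1 is not affected.** The conflict between pre-dose and pre-and-post-dose fluid begins in Cycle 2.
- **The laboratory result is not the only safeguard.** Judged risk is a second route in two of the three texts, and footnote S names patients still at risk as an example for repeat testing. A missed test need not mean missed hydration.
- **Eligibility.** A reader might infer that patients who cannot take the fluids pass Section 3.2, or that it excludes only NYHA class III or IV heart failure. Exclusion 9 covers impaired cardiac function broadly, exclusion 13 covers illness that impairs tolerance of treatment, and Section 3.1 sets LVEF and renal thresholds. Many such patients would be caught. What stands is that an explicit ineligibility rule is missing from the eligibility lists.
- **Section 6.4.1.** It says "The total volume of fluids may be adjusted as clinically indicated in subjects with baseline cardiac failure". A reader might take this to contradict the ineligibility rule. It need not: baseline cardiac failure can be present without making the programme contraindicated.
- **Effect on safety results.** A reader might infer that event rates will differ by which section a site followed. The documents give no figure from which to estimate that.

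**Conclusion.** The inconsistency is real and lies in the current text. For a triggered patient, Section 5.1.2 and footnote J give 3 to 6 L in Cycle 2 and Section 8.2.4 gives 1.75 to 3.5 L. From Cycle 3, Section 5.1.2 allows up to 3 to 6 L per cycle at discretion, and the other two specify no IV fluid. An untriggered, low-risk patient gets 250 to 500 mL after the Cycle 2 Day 1 dose under Section 8.2.4 and none under the others. These figures assume six doses per cycle and the before-and-after reading of the repeated programme.

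The trigger is also out of step with the testing schedule, the at-risk route is missing from footnote J for IV fluid, and one eligibility rule is absent from the eligibility lists. None of this touches the sample size or the response-rate analysis. It concerns whether a safety measure is delivered uniformly, and it should be corrected because sites following the protocol as written would give different fluid loads.

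**What to change.** The sponsor should:

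1. Reconcile Section 5.1.2, Section 8.2.4 and Appendix E footnote J to one statement of duration, timing around each dose, and entry routes (laboratory result, judged risk, or both), including whether post-dose fluid on Cycle 2 Day 1 applies to every patient.
2. Align that trigger with the testing rules in Section 7.3.5, the schedule grid and footnotes C and S, so that they agree with it and with each other.
3. Make Section 3.2 and the synopsis agree with Section 5.1.2 on patients in whom hydration is contraindicated.

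Which hydration, testing or eligibility rule stands is for the sponsor to decide; none is proposed here. The cost is amendment wording. Section 7.3.5 already schedules blood sampling on Cycle 2 Day 1, so aligning the tests with the trigger need not add a visit, whichever way the sponsor decides.
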